- The risks from infusion of micromolar amounts of exendin-(9-39) are remote. In rare cases, nausea and vomiting have been reported as possible side effects for Ex-9. The IND has been obtained from the FDA for the infusion of exendin-(9-39) [#65837] into humans. The Principal Investigator for the present study has used this peptide in several previous studies, in doses similar to those described in this application, with no attributable adverse effects observed. Allergic reactions to synthetic peptides are possible; therefore skin testing will be performed on each subject to assess sensitivity prior to undergoing any clamp procedures. All peptides will be synthesized to GMP standards and documented sterile and pyrogen free.
- The maximum amount of blood to be withdrawn during any one of these infusion procedures is approximately 141 ml and does not constitute an undue risk in persons with normal hematocrits.
- At study entry, women of child-bearing potential will have a serum pregnancy test. The pregnancy test must be negative before the subject can undergo any study testing.
- AIM-2: Some side effects of dexamethasone may include upset stomach, headache, dizziness, insomnia, restlessness, increased appetite or weight gain may occur.

This is not a complete list of possible side effects. If the participant notices other effects not listed above, they will be advised to contact the study physician.

Costs to the Subject

• Describe and justify any costs that the subject will incur as a result of participation; ordinarily, subjects should not be expected to pay for research without receiving direct benefit.

There will be no costs to participants for any of the treatments or testing done as part of this research study. Immediate necessary care is available if an individual is injured because of participation in a research project. However, there is no provision for free medical care or for monetary compensation for such injury. During this study, hospitalizations or additional care beyond the scope of this study will be the responsibility of patients and/or their insurance company.

Data Analysis & Statistical Considerations

Describe endpoints and power calculations. Provide a detailed description of how study data will be
analyzed, including statistical methods used, and how ineligible subjects will be handled and which
subjects will be included for analysis. Include planned sample size justification. Provide estimated time

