As the PI has performed similar studies with humans in the past, a Data Safety and Monitoring Plan (DSMP) has already been established for studies involving synthetic peptides such as exendin-(9-39). This DSMP will continue for the oversight of this project.

No toxicities of exendin-(9-39) or GLP-1 have been described in previous studies in humans. For the purposes of this study, a serious adverse event is defined as any of the following: death, life threatening event, or an event resulting in permanent disability, hospitalization, or prolongation of a hospital stay. Thus, the intervention and protocol represents slightly more than minimal risk to the research subjects. Due to the low risk status of this study, the data safety monitoring plan (DSMP) for this project represents the monitoring for adverse events by the principal investigator (PI) in conjunction with a Safety Officer.

The Safety Officer for this trial will be [name]. [name] is a practicing Cardiologist who has experience in trial design and clinical trials involving diabetes and carbohydrate metabolism. He is familiar with the procedures used in this project and is very familiar with the mechanisms for reporting adverse events. As Safety Officer, [name] will review the reports sent to him by the PI or his designees and will determine whether corrective action should be communicated to the PI, the IRB, the GCRC, NIH, and the FDA. The Safety Officer will be available to discuss glycemic control strategies with respect to the individual subject's medical care goals and the goals necessary for the study. If the goals and strategies necessary for the study exceed those necessary for medical care or practical for that individual, the PI and /or Safety Officer may choose to exclude the subject or discharge them from the study. Annually or at the completion of an Aim, the Safety Officer will complete a checklist that is used as a reminder regarding the functions he is to perform. We will prospectively collect data regarding potential adverse events during the course of the study and collate them on an annual basis. Since the PI and study team at the Center for Living will have frequent contact with the subjects, they are ideally suited to document the presence of Adverse Events.

There are a number of expected adverse events which will not be documented. These include mild hypoglycemic reactions, transient nausea and/or dizziness, and bruising/phlebitis at IV sites as these do

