not qualify as serious adverse events in this project. For the purposes of this study, a serious adverse event is defined as any of the following: death, life threatening event, or an event resulting in permanent disability, hospitalization, or prolongation of a hospital stay. These will be documented and reviewed by the safety officer as they arise.

In this low risk protocol, it is very unlikely that excess adverse events would occur that would require stopping the study. As outlined elsewhere, adverse events will be monitored and reviewed by the Safety Officer who would make any determination regarding stopping the protocol because of unacceptable risks to subjects. In addition, it is very unlikely that new information would become available during the study that would affect the protocol's integrity. This information would be captured on the Safety Officer Checklist which is reviewed annually or at the completion of an Aim.

In accordance with federal regulations the PI will monitor for, review, and promptly report to the IRB, appropriate institutional officials, sponsor, coordinating center and the appropriate regulatory agency head all unanticipated problems involving risks to subjects or others that occur in the course of a subject's participation in a research study, and all reportable AEs will be submitted per the DUHS IRB policies.

Describe Role of External Personnel:

Not applicable.

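### The monitoring plan rules out recording transient nausea and dizziness and mild hypoglycaemia, two of which overlap listed effects of Ex-9 or dexamethasone, and this conflicts with its own promise to collect adverse events

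*Combined protocol and SAP*

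**What the plan says.** All the relevant text is in two sections of the combined protocol and SAP.

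*Data & Safety Monitoring.* The plan makes a general promise: "We will prospectively collect data regarding potential adverse events during the course of the study", with annual collation. The Safety Officer reviews reports sent by the investigator or designees, and later in the section: "adverse events will be monitored and reviewed by the Safety Officer who would make any determination regarding stopping the protocol". Between these statements comes the exclusion: "There are a number of expected adverse events which will not be documented". The list opens the next sentence: "These include mild hypoglycemic reactions, transient nausea and/or dizziness, and bruising/phlebitis at IV sites as these do". That sentence then gives the ground for the exclusion, in the words "not qualify as serious adverse events in this project". Only serious events are expressly to be documented and passed to the Safety Officer as they arise. Unanticipated problems and reportable adverse events go to the IRB and others under institutional policy. The section also says: "No toxicities of exendin-(9-39) or GLP-1 have been described in previous studies in humans".

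*Risk/Benefit Assessment.* For the antagonist: "In rare cases, nausea and vomiting have been reported as possible side effects for Ex-9". For Aim 2: "Some side effects of dexamethasone may include upset stomach, headache, dizziness, insomnia, restlessness", followed by increased appetite and weight gain.

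**The concern.** The exclusion is a stated rule, so it cannot be read as a detail left for a manual. It tells staff not to record certain events, and two of those are events the protocol expects the study agents might cause. The reason given, that the events are not serious, justifies handling them without urgency. It does not justify leaving them out of the record.

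At stake is a plain description of tolerability. Ex-9 is given under an IND to every participant in both aims, and one Aim 2 group also takes dexamethasone for about a week. If the rule is followed, nobody can later say how often transient nausea or dizziness occurred, whether it began before or after Ex-9 was started, or whether it was commoner with dexamethasone or in a particular Aim 3 cohort. The person responsible for a stopping decision would not have this information either.

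**Working it through.** The point rests on the text and on no sample size, power or event rate. The plan gives no figure to reproduce.

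**Step 1. Named exclusions against listed effects.**

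| Excluded from documentation | Listed for Ex-9? | Listed for dexamethasone? |
|---|---|---|
| Nausea, if transient | Yes (nausea) | Partly, at most (upset stomach) |
| Dizziness, if transient | No | Yes |
| Mild hypoglycaemia | No | No |
| IV-site bruising or phlebitis | No (IV-placement risk) | No |

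The overlap with drug effects is therefore nausea for Ex-9 and dizziness for dexamethasone. Vomiting, persistent nausea, headache, insomnia, restlessness, increased appetite and weight gain are not named as excluded.

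**Step 2. Does another statement restore recording?** The general promise of prospective collection comes shortly before the exclusion, and the exclusion is the more specific of the two, so staff would follow the exclusion. The reporting routes for serious events, unanticipated problems and reportable events are unlikely to pick up events labelled expected and non-serious. The Safety Officer sees what is reported, and an undocumented event has no stated way into a report. Nothing in the documents restores recording of the named events.

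**Step 3. Scale.** Inputs from Design & Procedures: 20-25 completers in Aim 2 with two Ex-9 infusions each, and 15-20 in Aim 3 with one.

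- Low end: 20 × 2 + 15 = 55 infusions.
- High end: 25 × 2 + 20 = 70 infusions.

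The documents give no rate for transient nausea; they describe nausea and vomiting with Ex-9 as rare. The rates below are assumptions. Expected events = n × r. Chance of at least one = 1 − (1 − r)^n, treating infusions as independent, which is approximate because Aim 2 subjects contribute two.

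| Assumed rate per infusion | Expected events, n = 55 to 70 | Chance of at least one | Recorded under the rule |
|---|---|---|---|
| 0.1% | 0.06 to 0.07 | 5% to 7% | 0 |
| 1% | 0.55 to 0.70 | 42% to 51% | 0 |
| 5% | 2.8 to 3.5 | 94% to 97% | 0 |
| 10% | 5.5 to 7.0 | over 99% | 0 |

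The last column is the finding, and it does not depend on the rate. An infusion count does not measure exposure to dexamethasone, which is taken between visits; there the unit is the subject.

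**Step 4. What recording could show.** Aim 2 plans 10-15 dexamethasone subjects and 6-10 controls. For a two-sided Fisher exact test at 0.05, with assumed true proportions:

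| Dexamethasone v control | Power, 15 v 10 | Power, 10 v 6 |
|---|---|---|
| 30% v 10% | 7% | 3% |
| 40% v 10% | 23% | 9% |

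Complete logging would support a descriptive table and no useful test.

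**The case against.** The strongest reply is that this is a small physiology study with no safety endpoint, that the excluded events are mild and short-lived, and that the list is narrow. Much of this stands. A reader might infer that all expected drug effects have been removed from the record, or that the study could report no adverse events at all for Ex-9 or dexamethasone. The documents do not support that: most listed dexamethasone effects, and vomiting for Ex-9, are not named. The list does open with a word that leaves it unclosed, and its reason would fit any non-serious event, but reading it that widely would empty the promise of prospective collection.

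Two further limits also stand. Hypoglycaemia is not listed for either agent, and blood glucose is measured every 5-10 minutes during the clamp and once afterwards. A low value at the visit would therefore appear in the glucose data, although symptoms would not. And lack of power to detect an excess comes mainly from group size and design. Ex-9 always follows the glucose-only hour and no infusion omits it, so attribution would stay weak even with full records.

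It might also be said that the established monitoring plan to which the section refers has its own forms. Those forms are not in the documents, and the text that is there says the opposite.

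What the reply does not answer is the contradiction itself. The section promises to collect adverse events and then forbids recording some that the protocol attributes to its own agents.

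**Conclusion.** The point holds for the named events. By rule, their recorded count is zero over 55 to 70 planned infusions whatever the true rate, and the Safety Officer has no stated route to them. This rests on the exclusion being followed as written and on no unseen form overriding it. It should be changed, because the conflict is explicit and the remedy is small.

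Two stronger readings should be set aside. One is that the rule is what prevents an excess being detected: with 10-15 against 6-10 subjects, formal detection is largely out of reach in any case, and what the rule costs is the description. The other is that the rule leaves the statement about no toxicities untestable, or that Risk/Benefit Assessment plainly refutes it. That statement concerns earlier human studies, which logging in this trial cannot test, and whether rare nausea counts as a toxicity is arguable. The two sentences sit uneasily together and should be aligned as a separate matter of wording.

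**What to change.** 1. In Data & Safety Monitoring, delete the statement that some expected events go undocumented, so that the section agrees with its own promise of prospective collection.
2. Log mild hypoglycaemic reactions, nausea, dizziness and IV-site events on the visit form, with visit, arm or cohort, and severity. For events during the clamp, add onset time relative to the start of Ex-9.
3. At Visit 3 in Aim 2, ask one recall question about the preceding week, worded identically for dexamethasone and control subjects. Effects of dexamethasone arise between visits, so observation at the infusion alone would miss them.
4. Give the Safety Officer a descriptive table by dexamethasone or control and by Aim 3 cohort at the existing review, annually or at completion of an aim. State that it is not for formal testing.
5. Keep immediate handling for serious events only, as now.
6. Align the sentence on toxicities with the side effects listed under Risk/Benefit Assessment.

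The cost is a few form lines, one question and a short table. A nurse is already present at the infusions, glucose is already sampled, and the Safety Officer review already exists. No visit, procedure or clinical rule changes.
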